The *Stanford Binet Intelligence Scales, 5th Edition* (SB-5)(Roid, 2003) will be used to assess verbal, nonverbal, and overall cognitive abilities and will be administered at the baseline assessment. The SB5 will be used to confirm that the adolescent participant meets the inclusion criteria of a full-scale IQ >70 and will also be used as a predictor in statistical analyses. As noted, this will only be collected at the first baseline time point for both groups.

Baseline, Post-Treatment, and 6-Month Follow-Up:

The *Vineland Adaptive Behavior Scales, 3rd Edition* (Vineland-3)(S. Sparrow et al., 2016) is a well-established standardized measure of adaptive behavior that assesses skills in the Communication, Daily Living Skills, and Socialization domains. The DLS domain is comprised of the Personal, Domestic, and Community subdomains and has items that directly correspond to goals being targeted in the STRW intervention. The Vineland-3 will be used at screening to confirm that the adolescent has deficient DLS (i.e., at least 1 of the 3 DLS subdomain standard scores is at least 15 points or more below full scale IQ). Raw scores and age equivalent scores on the DLS domain and subdomains will be used as a primary outcome measure.

The *Daily Living Skills Goal Attainment Scale (DLS-GAS)(Ruble, McGrew, & Toland, 2012)* will be created for each adolescent based on an in-depth clinical interview completed with the parent that assesses specific skills in all of the goals that will be targeted in the STRW intervention. The DLS targeted in STRW will be explicitly defined for each participant using GAS based on their current skill level. For example, for the targeted skill of laundry, parents will be asked to describe their adolescent's ability to independently separate clothes, use the washing machine and dryer, and fold and put clothes away. An independent clinical research coordinator who will not participate in any aspect of the STRW intervention will develop the DLS-GAS for each adolescent participant and evaluate change in goals on the DLS-GAS at post-treatment and 6-month follow-up assessments. The therapists facilitating the STRW intervention will not have access to the DLS-GAS. The DLS-GAS will be utilized as a primary outcome measure.

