A secure REDCap⁸⁰ database has been built and will be maintained for all measures administered in the current study. The primary analysis will be conducted with an intent-to-treat approach. The primary outcome measures for Objectives 1 and 2 at post-treatment and 6-month follow-up are (1) change in Vineland-3 DLS domain raw score and age equivalent score and (2) change in score on the goals targeted on the DLS-GAS. We will also evaluate the Vineland-3 subdomain raw scores and age equivalent scores. The expectation is that the STRW group will have an increased change in score on both the Vineland-3 and DLS-GAS as compared to the control group. All analyses will be done using SPSS Version 20.0. Univariate statistics such as means, medians, and standard deviations will be computed for each variable to allow for examination of any outliers, variables that are not normally distributed, and heterogeneous variance between groups. The comparability of the two groups in some measured baseline covariates prior to treatment will be assessed using chi-square tests for categorical variables and t-tests for continuous variables. Variables found to be non-normal will be transformed using appropriate functions to confirm with the normality assumptions.

To test Aim 1: Initially a two-sample t-test will be used to test the difference on the change scores in the Vineland-3 DLS domain and GAS (post-treatment and baseline) between the STRW and control groups. Although this is a randomized study it is possible that some of the demographic variables might be differentially distributed between the groups. In this case, the initial analysis will be followed by a general linear regression analysis where cohort will be treated as the main effect and other differentially distributed variables will be added to the model as possible confounders in order to investigate the independent effect of the intervention group on outcome.

To test Aim 2: The within-subject change between post-treatment and 6-month follow-up for each individual receiving the intervention will be calculated and a paired t-test will be conducted to evaluate this change (post-treatment and 6-month follow-up).

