To test Aim 3: Exploratory analyses will be conducted to examine the relationship between progress in DLS and executive functioning, social skills, and parenting and family factors. A regression analysis will be used to estimate and examine this potential relationship. In this model the change score (post-treatment and baseline) will be modeled as a function of each of the measures of executive function, social skills and parenting and family factors. This will allow us to characterize the response profile.

Missing data methods

All missing data will be discussed and every effort will occur to ensure all data are accounted for. Parents will be given multiple opportunities to fill out parent-report forms. To minimize possible loss to follow up, we will stay in close contact with families and identify any potential barriers to successful completion. Despite these efforts, missing data may occur. We will first examine the missing pattern to determine if missingness occurs systematically and differentially for each group, and tabulate the reason for missingness. Assuming at random, we will use multiple imputation technique to generate multiple datasets and systematically combine the estimates obtained from each dataset and associated variability. We will also investigate the potential that the missingness is not at random by performing sensitivity analysis recommended for clinical studies. Suspected biases will be taken into account in the interpretation of results.

Sample Size and Power Calculations

The pilot RCT is being conducted with the intent of examining the differences in DLS to be expected. Few studies have examined the trajectory of DLS in individuals with ASD(Baghdadli et al., 2012; Bal et al., 2015; Szatmari et al., 2009), and no studies have examined how DLS develop during adolescence. Power calculations focused on the anticipated increase or improvement in the age equivalence scores of each of the Vineland-3 DLS subdomains for the STRW group and control group. We used conservative estimates of change in DLS subdomain age equivalence scores for our sample size estimation, even though a recent pre-post trial on STRW with 7 participants found a mean improvement of 2.3 to 2.6 years across the 3 subdomains(Duncan et al., in press) from baseline to post-treatment.

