Aim 1: For each DLS subdomain, we anticipate that adolescents in the STRW group will have a mean improvement of 9 months (a mean gain in age equivalence of 9 months) at post-treatment compared to a mean improvement of 4 months in the control group. Assuming a conservative pooled standard deviation of 8.4, we will have 80% power to detect the above effect size (of 0.71) with 32 participants per group. We will have 90% power to detect an effect size of 0.82 (a 9.9-month difference in the change of age equivalents between groups).

Aim 2: For each DLS subdomain, we anticipate that all participants, after receiving the STRW treatment, will maintain treatment gains from post-treatment to 6-month follow-up.

FACILITIES and PERFORMANCE SITES:

The Division of Behavioral Medicine and Clinical Psychology (BMCP) at Cincinnati Children's Hospital Medical Center (CCHMC) will serve as the project site for the recruitment and assessment of participants for the study. Assessment rooms (approximately 225 sq. ft.) within DDBP will be used for the assessments. The video and audio recording equipment needed for the project will be housed in this space for the duration of the project.

The in-person STRW and control group sessions will be held in the Schubert Research Clinic through the Clinical Translational Research Center (CTRC) in the T building on CCHMC's campus. We will use 2 conference rooms for the parent and adolescent weekly meetings. We will be using the Metabolic kitchen for the cooking portion of the STRW group.

POTENTIAL BENEFITS:

We hope that all participants in the intervention group will benefit greatly from the individualized intervention in daily living skills provided in this study. We also hope it may increase skills in other areas and by incorporating parental involvement, potentially directly affect current functioning and future adult outcomes by increasing capabilities for skills that are needed to succeed in college, employment, and independent living. Further potential benefits for those enrolled in the PEERS intervention include hopefully improving the participant's social skills. However, it is important to

emphasize that this study is being conducted for research purposes and does not ensure better or safer treatment nor guarantee individual benefits to the participant. Participants will receive monetary compensation for their time spent completing the study protocol.

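### Power is stated for each Vineland-3 DLS subdomain, but Aim 1 tests the DLS domain and DLS-GAS, which have no power figure; the plan's own subdomain inputs give about 65%, not 80%

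*Combined protocol and SAP*

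**What the plan says.** Three sections of the combined protocol and SAP bear on this.

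- **Sample Size and Power Calculations.** The basis is the subdomain age equivalent: "Power calculations focused on the anticipated increase or improvement in the age equivalence scores of each of the Vineland-3 DLS subdomains". Under Aim 1, for each subdomain, the expected mean gains are 9 months (STRW) and 4 months (control), with a pooled SD of 8.4, and "we will have 80% power to detect the above effect size (of 0.71) with 32 participants per group". A further statement gives 90% power at an effect size of 0.82, described as a 9.9-month difference. Alpha and sidedness are not given.
- **Data Analysis/Methods, Analyses.** The primary outcomes are "1) change in Vineland-3 DLS domain raw score and age equivalent score" and "2) change in score on the goals targeted on the DLS-GAS". Subdomains follow as an addition: "We will also evaluate the Vineland-3 subdomain raw scores and age equivalent scores". For Aim 1, "a two-sample t-test will be used to test the difference on the change scores in the Vineland-3 DLS domain and GAS".
- **Measures, Vineland-3 entry.** "Raw scores and age equivalent scores on the DLS domain and subdomains will be used as a primary outcome measure". The DLS-GAS entry names that scale as a primary outcome measure as well.

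**The concern.** A power statement should describe the test by which the trial will be judged. Here the calculation concerns one set of scores (three subdomain age equivalents) and the Aim 1 t-test uses another (the DLS domain and the GAS). Subdomain power does not carry over:

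- The SD of domain change depends on how the three subdomains move together, which the plan does not give.
- A raw domain score is not measured in months at all.
- The DLS-GAS is a different instrument on its own scale.

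A null result on the domain or the GAS could therefore not be read against any planned sensitivity. The sections also disagree on whether the subdomains are primary, so a reader cannot tell which outcome the 80% is meant to protect. Finally, the 80% has to be checked before anyone carries it across to another outcome.

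**Working it through.** **Inputs.** From Sample Size and Power Calculations: gains of 9 and 4 months, SD 8.4, stated effect size 0.71, 32 per group. From Study Design: 35 per group to be enrolled. Assumed, because not stated: alpha 0.05, two-sided. Power is from the noncentral t distribution for a two-sample t-test. The normal approximation, power ≈ Φ(d·√(n/2) − 1.96), serves as a check.

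**1. The plan's figure, taken from its printed effect size.** With d = 0.71 and n = 32, power is 79.8% (normal approximation: 0.71 × 4 − 1.96 = 0.88, giving 81.1%). With d = 0.82, power is 89.8%. The stated 80% and 90% therefore follow from the printed effect sizes.

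**2. The same figure, taken from the plan's means and SD.** d = (9 − 4)/8.4 = 0.595, not 0.71.

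| n per group | Power at d = 0.595, two-sided 0.05 |
|---|---|
| 32 | 65.0% (normal approximation 66.3%) |
| 35 | 69.0% |

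About 46 per group would be needed for 80%. A one-sided 0.05 test does not rescue the figure: 76.1% at 32 and 79.4% at 35. At SD 8.4, d = 0.71 means 0.71 × 8.4 = 6.0 months and d = 0.82 means 6.9 months, not 9.9. To make 5 months equal d = 0.71, the SD would have to be 5/0.71 = 7.04.

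**3. What this implies for the DLS domain.** The documents give no domain figures, so this step is an illustration. Assume domain change behaves like the mean of three subdomain changes with equal SDs, a common mean difference and common pairwise correlation r. Then SD(domain) = 8.4 × √((1 + 2r)/3), and the domain effect size is the subdomain effect size divided by √((1 + 2r)/3). At 32 per group:

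| r | Domain SD | d from 5 months | Power | Domain d if subdomain d = 0.71 | Power |
|---|---|---|---|---|---|
| 0.3 | 6.13 | 0.815 | 89.4% | 0.972 | 96.9% |
| 0.5 | 6.86 | 0.729 | 81.9% | 0.870 | 92.8% |
| 0.7 | 7.51 | 0.665 | 74.6% | 0.794 | 87.8% |
| 0.9 | 8.12 | 0.616 | 67.9% | 0.735 | 82.5% |

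Because √((1 + 2r)/3) cannot exceed 1, the domain never has less power than a single subdomain under this model. With the printed 0.71 every entry is above 80%. Entries below 80% appear only with 0.595, so they come from the arithmetic inconsistency in step 2 and not from the change of outcome.

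**4. What this implies for the DLS-GAS.** Nothing can be derived. For assumed effect sizes of 0.3, 0.5, 0.7 and 1.0, power at 32 per group is 22%, 50%, 79% and 98%. The effect detectable with 80% power is 0.71 at 32 per group and 0.68 at 35, for any continuous outcome compared by this t-test.

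**The case against.** The strongest reply has four parts.

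- **The powered outcome is one the plan calls primary.** The Measures section lists the subdomains together with the domain. This stands in part: it would be too broad to say that the plan has no power figure for any outcome it calls primary. But the same sentence includes the domain, and the DLS-GAS is primary in both sections, so two primary outcomes still lack a figure. The Aim 1 test does not use the subdomains.
- **Changing from subdomain to domain may help.** This stands. A reader might infer from the mismatch that the trial is underpowered for the domain. The documents do not support that: they give no domain SD and no correlation, and under the averaging model the domain does at least as well as one subdomain.
- **In standardised terms, 0.71 at 32 per group applies to any outcome.** This is correct as a detectable effect. It does not say whether an effect of that size is expected on the domain or the GAS, and the plan links it to months of subdomain gain that do not produce it.
- **This is a pilot.** That softens the consequence. The plan nevertheless claims 80% and 90% power and runs significance tests on named primary outcomes.

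A reader might also infer that Aim 1 succeeds only if both the Vineland-3 and the GAS succeed, and that joint power is lower still. The plan states no such rule. Aim 1 asks for significant improvement on the Vineland-3 but only progress on the GAS, so no joint-power figure is warranted.

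**Conclusion.** The point holds as two linked findings. The stated power does not describe the Aim 1 test: it is for subdomain age equivalents, while the test is on the DLS domain and DLS-GAS, and the sections disagree on which Vineland-3 scores are primary. Separately, the plan's own 5-month difference and SD of 8.4 give about 65% power at 32 per group (69% at 35), not 80%. On those inputs domain power would lie between 68% and 89%. Power for the DLS-GAS is unknown.

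The 65% and 69% rest on an assumed two-sided alpha of 0.05. The domain range rests also on the averaging model, equal SDs and correlations of 0.9 to 0.3, none of which the documents give. The finding is that power for the primary test is unstated and the stated figure is internally inconsistent. It is not that the trial is shown to be too small for its primary outcomes. It should be corrected, but does not invalidate the design.

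**What to change.** 1. Reconcile the Measures and Analyses sections on which Vineland-3 score is the Aim 1 primary: domain or subdomain, raw or age equivalent.
2. Restate power for that outcome with the assumed difference, the SD and its source, and alpha with sidedness.
3. Add for the DLS-GAS either a power statement with its assumptions or a detectable effect (0.71 with 80% power at 32 per group).
4. Correct the subdomain figure so that it agrees with 9 versus 4 months and SD 8.4, or change and justify those inputs. It should not stay at 80% as it is. Align the 9.9-month figure with its effect size of 0.82. If the domain is chosen as primary, label subdomain power as secondary.
5. Give no joint power unless the plan adopts a rule that both outcomes must succeed.

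The cost is a recalculation and a paragraph of text, with no extra participants. The downside is that the stated power may be less favourable than 80%.

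### The 80% power claim does not follow from the plan's own inputs: 9 versus 4 months at SD 8.4 is an effect size of 0.60, not 0.71, which gives about 65% power with 32 per group; the 9.9-month figure does not fit either

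*Combined protocol and SAP*

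**What the plan says.** The sample size section bases its power calculation on change in age-equivalent scores for each Vineland-3 daily living skills subdomain. Under Aim 1 it expects STRW participants to gain 9 months on average, and sets this against the other arm: "compared to a mean improvement of 4 months in the control group". The power claim that follows rests on a "conservative pooled standard deviation of 8.4, we will have 80% power to detect the above effect size (of 0.71) with 32 participants per group". A second scenario then reads: "We will have 90% power to detect an effect size of 0.82 (a 9.9-month difference in the change of age equivalents between groups".

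The analysis section gives the matching test for Aim 1: "Initially a two-sample t-test will be used to test the difference on the change scores". It is unadjusted; regression follows only if demographic variables turn out to be unevenly distributed. The Study Design section sets enrolment at 35 per group or more. The power text gives no alpha, sidedness, dropout allowance, pre-post correlation or covariate adjustment.

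**The concern.** The wording ties 0.71 to the means and SD just given, yet those inputs produce 0.60. The next sentence also pairs an effect size with a month difference that the same SD does not support. Both of the paragraph's conversions between months and standardised effect therefore fail.

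This is the only numerical justification of the sample size. If the printed means and SD are what the investigators meant, the chance of missing the advantage they expect is about 35%, not 20%. A non-significant result would then be read against a sensitivity that the trial lacks. The figures may also be reused to size a later trial, a natural use of a pilot, and would make that trial too small.

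**Working it through.** **Inputs.** From Sample Size and Power Calculations, Aim 1: gains of 9 and 4 months, SD 8.4 (unit not printed, read as months), 32 per group, effect sizes 0.71 and 0.82, and 9.9 months. From Study Design: 35 per group. From Analyses: two-sample t-test on change scores. Assumed: two-sided alpha 0.05.

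**Method.** Effect size d = difference / SD. Power comes from the noncentral t distribution with 2n − 2 degrees of freedom and noncentrality d × √(n/2), where n is the number per group. For n = 32, √(32/2) = 4, there are 62 degrees of freedom, and the critical value is 2.00.

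**Step 1: the plan's figures, taking its effect sizes as given.**
- d = 0.71: noncentrality 0.71 × 4 = 2.84, power 79.8%.
- d = 0.82: noncentrality 0.82 × 4 = 3.28, power 89.8%.

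Both match the stated 80% and 90%. Solving for the detectable effect with 32 per group gives 0.711 and 0.823. The effect sizes, sample size and power therefore agree with one another, and they do so under a two-sided 5% test.

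**Step 2: the plan's months and SD.**
- d = (9 − 4) / 8.4 = 5 / 8.4 = 0.595.
- Noncentrality with 32 per group: 0.595 × 4 = 2.38.

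| Per group | Power, two-sided 5% | Power, one-sided 5% |
|---|---|---|
| 32 | 65.0% | 76.1% |
| 35 | 69.0% | 79.4% |
| 36 | 70.2% | 80.4% |

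The normal approximation gives 66.3% (two-sided) and 76.9% (one-sided) at 32 per group. With the two-sided t-test, 80% power needs 46 per group and 90% needs 61.

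**Step 3: what would make 0.71 true.**
- At SD 8.4: 0.71 × 8.4 = 5.96 months, not 5.
- At 5 months: 5 / 0.71 gives SD 7.04, not 8.4.

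**Step 4: the 90% scenario.**
- 0.82 × 8.4 = 6.9 months, so 9.9 is 3.0 months too large.
- 9.9 / 8.4 = 1.18, which would have over 99% power with 32 per group.
- 9.9 / 0.82 = 12.1, the SD needed for 9.9 months to equal 0.82.
- At the SD of 7.04 from Step 3, 0.82 is 5.8 months.

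No single SD rescues both sentences: one needs 7.04 and the other 12.1.

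**The case against.** The strongest reply is that the documents show a contradiction but not which number is wrong. The 80% does follow from 0.71. A 6-month difference at the printed SD gives 6 / 8.4 = 0.714 and 80.3% power, and 0.82 is then 6.9 months, one digit from the printed 9.9. The month figures could thus be misprints and the design sound. This stands as a limit on the claim: 65% is the power of the figures as printed, and may not be that of the calculation the investigators ran. It does not clear the paragraph, because the 4-month control gain is printed plainly and nothing in the text supports a 6-month difference.

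Other possible rescues fall short:
- **One-sided test.** Power is 76% with 32 per group and reaches 80% only at 36. The plan states no one-sided test, its 80% is tied to 32, and 5 / 8.4 would still not be 0.71.
- **SD of a single time point.** If 8.4 were such an SD, the change-score SD would be 8.4 × √(2(1 − r)), which equals 7.04 at a pre-post correlation r of about 0.65. The plan mentions no correlation, and 9.9 months would still not fit.

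Two points of scale are fair. The calculation concerns subdomain age equivalents, whereas the Analyses section names the DLS domain score and the DLS-GAS as primary, so 65% is not the power of the primary comparisons. And with a document dated November 2022 and a study due to end in December 2022, this is a correction to the record that leaves enrolment and analyses unchanged. That a null result would be misread is a risk, not something the documents establish.

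**Conclusion.** The concern holds. The printed months, SD and effect sizes cannot all be correct, and no reading found in the documents reconciles them. Taken as printed, the anticipated 5-month advantage is an effect of 0.60 with about 65% power at 32 per group (69% at 35), against a claimed 80%. The 32 per group on which the plan bases its 80% is 14 short of the 46 required. The month difference quoted for 90% power is overstated by 3.0 months if SD 8.4 is right.

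The power figures assume a two-sided 5% t-test on change scores, equal groups, and 8.4 months as the SD of change. The two-sided level is well supported, since it is the one at which 0.71 and 0.82 return the plan's own 80% and 90%. The mismatch between months and effect sizes depends on neither alpha nor sidedness.

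**What to change.** The sponsor should trace which input slipped and restate the Aim 1 power paragraph so that means, SD (with its unit, and whether it is the SD of change), effect size, alpha, sidedness and power agree.

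- **If 9, 4 and 8.4 are right:** a 5-month difference with SD 8.4 (d = 0.60) has about 65% power with 32 per group and 69% with 35 at two-sided 5%; 32 per group gives 80% power for 6.0 months (d = 0.71) and 90% for 6.9 months (d = 0.82).
- **If the SD should be about 7.04:** correct it, give its source, and restate the 90% difference as 5.8 months.
- **If the anticipated difference should be 6 months:** correct the group means and restate the 90% difference as 6.9 months.

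The cost is one reworded paragraph, and in the first case a less favourable power statement. No extra enrolment or change of analysis is needed to correct it. Any report or later sample size calculation that draws on this paragraph should use the corrected figures.
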